#### **Research Protocol**

## I. Aims

The purpose of the study is to evaluate the efficacy of Ropinirole in treatment of muscle cramps in patients with cirrhosis.

## **II. Background and Rationale**

Muscle cramps are common in liver disease, especially in patients with cirrhosis. The prevalence of muscle cramps among patients with chronic liver disease is estimated to be 22-88%. Patients with cirrhosis who experience muscle cramps report that they are extremely painful and they often occur at rest and frequently during sleep. The severity of muscle cramps in some patients has resulted in presentation to an acute care facility for pain relief with short acting opioids. Muscle cramps impact many areas of life including sleep, physical functioning and mobility, general health, mental health, energy levels and social isolation. Despite the association of muscle cramps with liver disease, there is a paucity of information regarding treatment in these patients. Many treatment options have been reported in the literature but no standard of treatment has been established. Different options include Zinc, 1-alpha-hydroxy Vitamin D, Vitamin E, branched chain amino acids, taurine, L-carnitine, eperisone hydrochloride, intravenous albumin and quinidine. Oral vitamin E replacement has been used successfully in the management of nocturnal muscle cramps in cirrhotic patients. In a group of 23 cirrhotic patients (16 and 7 Child's-Pugh category A and B respectively), oral vitamin E (tocopherol acetate) 200 mg t.i.d. significantly improved the frequency, duration and pain associated with nocturnal cramping without untoward effects. Quinine and quinidine have also been used with success in the treatment of cirrhosis-associated muscle cramps, but their potential for cardiac and gastrointestinal toxicity make them less desirable therapeutic choices. Similarly, another study comparing the effect of 325 mg of quinine versus vitamin E 400 IU at bedtime found reduction in frequency of leg cramps to 3.6 and 3.3% respectively (95% confidence interval, -3.8, +3.2), suggesting similar efficacy. Considering the potential toxicity of quinine, vitamin E is recommended as the initial treatment of choice for patients on dialysis with leg cramps. Our aim is to compare the efficacy of Ropinirole, to Vitamine E in the treatment of these cramps in cirrhotic patients. Ropinirole is primarily used for treatment of restless leg syndrome. However, off label trial of low-dose Ropinirole in clinical practice has shown some success in providing relief of muscle cramps in patients with cirrhosis.

### . Procedures

A. Research Design: Prospective Randomized cross-over design

## B. Sample

- a. Number of subjects: 60; 30 in Group A; 30 in Group B
- b. Inclusion criteria: Patients age >/= 18 years of age with diagnosis of cirrhosis who self-report regular muscle cramping.
- c. Exclusion criteria: patients without cirrhosis, patients under age 18, pregnant women

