### C. Study procedures

- a. Patients will be recruited from a panel of patients at Vanderbilt University Medical Center Hepatology clinics. Patients meeting inclusion criteria will be randomized to two groups; group A (Vitamin E 400 I.U) or group B (Ropinirole). Patients will remain in their prospective groups until 3 months at which time they will be switched to the other group. Total study duration will be six months. Patient demographics to be collected include patient age, gender, height, weight, BMI, race/ethnicity, etiology of cirrhosis. Baseline lab data to be collected include Magnesium, Potassium, Albumin, and total bilirubin. Child-Turcotte-Pugh class will be calculated using the five measures of severity of chronic liver disease (Total bilirubin, INR, albumin, presence of ascites or hepatic encephalopathy). Baseline data regarding diuretic usage including Furosemide, Spironolactone, Bumex, Metolazone, Inspra will be obtained. A survey (attached) will be given to each group of patients in the beginning of the study period and 3 and 6 months after study initiation.
- b. Participants will be given a prescription for Ropinirole. Vitamin E will be provided by the GI clinical research office at no cost to the patients.
- c. Adverse event reporting: Serious adverse events will be reported to the VU IRB per VU IRB policy. All adverse events will be captured and reported to the VU IRB at the time of continuing renewal or upon study closure, whichever occurs first.
- d. Withdrawal procedures: If a patient suffers an adverse event, which in the judgment of the investigator is an unacceptable consequence or risk to the patient, the patient can be withdrawn from the study. Patients may withdraw from the study at any time for any reason, and without prejudice to further treatment. A patient can withdraw their consent to participate in the study at their own request or be withdrawn from participation in the study at the request of their legally authorized representative at any time for any reason.
- e. Privacy and confidentiality issues: Consent will be obtained by the study personnel in a private location within the TVC. No PHI will be collected prior to obtaining informed

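### The month-3 switch has no pregnancy re-check, so a vitamin E patient who unknowingly conceives in period 1 would newly start ropinirole

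*Combined protocol and SAP*

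**What the plan says.** B. Sample, item c, gives the only mention of pregnancy in the supplied text: "Exclusion criteria: patients without cirrhosis, patients under age 18, pregnant women". The inclusion criterion sets a minimum age of 18 but neither an upper age limit nor a restriction by sex, so women able to become pregnant are eligible.

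C. Study procedures, item a, randomises patients to "group A (Vitamin E 400 I.U) or group B (Ropinirole") and keeps them there "until 3 months at which time they will be switched to the other group". No condition is attached to the switch. The only assessment named at that time is the survey: "A survey (attached) will be given to each group of patients in the beginning of the study period and 3 and 6 months". Item f adds a follow-up at month 3 but does not describe its content.

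Item b says "Participants will be given a prescription for Ropinirole", without saying when it is written or what is checked first. Item d gives the investigator one stated ground for withdrawing a patient: "If a patient suffers an adverse event, which in the judgment of the investigator is an unacceptable consequence or risk to the patient". Patients, or their legal representatives, may also end participation for reasons of their own. Pregnancy is not named in item d.

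**The concern.** Pregnancy differs from the other two exclusions. A diagnosis of cirrhosis and an age of 18 or over do not normally reverse during a six-month trial. Pregnancy can begin after entry, and the patient may not know of it.

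The crossover makes this matter, because half the patients first receive ropinirole three months after eligibility was judged. A check at entry, however thorough, cannot cover that second start. The protocol itself treats pregnancy as a reason not to receive study treatment, yet a site that followed the text exactly could begin ropinirole in a pregnant woman at month 3. What is at stake is the safety of a very small number of patients, not the comparison of the two drugs.

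**Working it through.** The plan states no figure on this point, so there is nothing to reproduce. The check has two parts.

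**Reading the sections together**

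1. B. Sample: pregnant women may not enter. No method or time of ascertainment is given.
2. C. Study procedures, item a: all patients change drug at month 3, and no eligibility re-check is stated.
3. Items a and f: a survey and a follow-up of unstated content are all that is named at month 3.
4. Item d: the investigator may withdraw a patient for an unacceptable adverse event. A pregnancy that nobody has recognised triggers neither that ground nor the patient's own decision to leave.

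On the supplied text, then, nothing stands between an unrecognised pregnancy in period 1 and the start of ropinirole in group A.

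**Size**

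Inputs from B. Sample: 60 patients, 30 per group. By the design, the 30 in group A start ropinirole at month 3. Two further inputs are not in the documents and are assumed:

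- *f*, the share of patients who are women able to become pregnant: 5% to 20%, equal in both groups on average.
- *p*, the chance that such a woman has an undetected pregnancy at month 3: 1% to 5%.

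All patients are taken to reach month 3; dropout would lower every count.

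Formulas:

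- Expected undetected pregnancies at the start of ropinirole in group A = 30 × *f* × *p*.
- Tests needed at month 3, both groups = 60 × *f*.
- Expected pairs lost if study drug is stopped on a positive test in either group = 60 × *f* × *p*. This applies the same *p* to group B women about to start vitamin E.

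| *f* (assumed) | Women in group A | Tests at month 3 | Ropinirole starts in group A, *p* = 1% / 5% | Lost pairs of 60, *p* = 1% / 5% |
|---|---|---|---|---|
| 5% | 1.5 | 3 | 0.015 / 0.075 | 0.03 / 0.15 |
| 10% | 3 | 6 | 0.03 / 0.15 | 0.06 / 0.30 |
| 20% | 6 | 12 | 0.06 / 0.30 | 0.12 / 0.60 |

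The extremes are 30 × 0.05 × 0.01 = 0.015 and 30 × 0.20 × 0.05 = 0.30 for ropinirole starts, and 60 × 0.05 × 0.01 = 0.03 and 60 × 0.20 × 0.05 = 0.60 for lost pairs. The largest loss is 0.60 / 60 = 1% of pairs.

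Group B's ropinirole starts at month 0 are left out of both counts. They fall under the entry exclusion, and a woman found pregnant before randomisation is not enrolled, so she is not a lost pair.

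**The case against.** The strongest objection is that part of the plan cannot be seen. The survey and the REDCap database are marked as attached but were not supplied, and the consent pages were removed. Any of them could carry a pregnancy question, a test or contraception advice. This applies to month 3 as much as to entry, because the same survey is given then. It stands: the finding concerns the supplied procedures only.

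Next, a recognised pregnancy has ways out. There is a visit at month 3, ropinirole needs a prescription, and a patient may leave when she chooses. That also stands, and it narrows the point to the unrecognised case. It does not remove it, because none of these steps would reliably find a pregnancy the patient is unaware of.

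The expected count is well below one, and both percentages behind it are assumed. This is true and settles the weight: low. It does not argue against a test that costs little and follows from the protocol's own exclusion.

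A reader might infer three stronger points, none of which the documents support:

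- *That pregnant women can be enrolled because no entry test is listed.* A site following B. Sample must already exclude them; only the method is unstated. The laboratory sentence ("Baseline lab data to be collected include Magnesium, Potassium, Albumin, and total bilirubin") is not a complete screening list. It omits INR, which the next sentence needs for the Child-Turcotte-Pugh class ("using the five measures of severity of chronic liver disease (Total bilirubin, INR, albumin"). Its silence shows little.
- *That the switch breaches the eligibility criteria.* The criteria govern entry. What is missing is a safeguard at the crossover.
- *That ropinirole is shown to be harmful in pregnancy.* The documents give no fetal-risk information for either drug.

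**Conclusion.** The point holds in a limited form. The supplied text has no pregnancy re-check at the month-3 switch and does not name pregnancy as a ground for stopping study drug, so a group A woman with an unrecognised pregnancy would newly start ropinirole.

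Under the assumed ranges, fewer than one such start is expected: 0.3 at most, and that only with both assumptions at their upper ends. The conclusion rests on the protocol's own decision to bar pregnant women, and on no re-check being specified in the unsupplied material.

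It is a cheap safety improvement of low weight. It does not affect the treatment estimate. The lack of a named test at entry calls for clarification only.

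**What to change.** Three small edits:

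- In C. Study procedures, item a: require a urine pregnancy test for women able to become pregnant at the existing 3-month follow-up, before the second drug is prescribed or supplied.
- In item d: state that study drug stops if pregnancy is found.
- As a clarification only, name in item a how pregnancy is ascertained at entry. If an attachment already specifies a test, cite it and add the month-3 re-check only if that is absent.

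The cost is about 3 to 12 inexpensive tests at a visit already planned, and two or three sentences of text. A woman stopped at month 3 contributes no second-period value to the paired t-test in D. Data Analysis; the expected loss is the 0.03 to 0.6 pairs derived above. The planned 60 patients need not change.

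One limit remains: a test at the switch does not cover a woman who conceives while already taking ropinirole.

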### C. Study procedures

- a. Patients will be recruited from a panel of patients at Vanderbilt University Medical Center Hepatology clinics. Patients meeting inclusion criteria will be randomized to two groups; group A (Vitamin E 400 I.U) or group B (Ropinirole). Patients will remain in their prospective groups until 3 months at which time they will be switched to the other group. Total study duration will be six months. Patient demographics to be collected include patient age, gender, height, weight, BMI, race/ethnicity, etiology of cirrhosis. Baseline lab data to be collected include Magnesium, Potassium, Albumin, and total bilirubin. Child-Turcotte-Pugh class will be calculated using the five measures of severity of chronic liver disease (Total bilirubin, INR, albumin, presence of ascites or hepatic encephalopathy). Baseline data regarding diuretic usage including Furosemide, Spironolactone, Bumex, Metolazone, Inspra will be obtained. A survey (attached) will be given to each group of patients in the beginning of the study period and 3 and 6 months after study initiation.
- b. Participants will be given a prescription for Ropinirole. Vitamin E will be provided by the GI clinical research office at no cost to the patients.
- c. Adverse event reporting: Serious adverse events will be reported to the VU IRB per VU IRB policy. All adverse events will be captured and reported to the VU IRB at the time of continuing renewal or upon study closure, whichever occurs first.
- d. Withdrawal procedures: If a patient suffers an adverse event, which in the judgment of the investigator is an unacceptable consequence or risk to the patient, the patient can be withdrawn from the study. Patients may withdraw from the study at any time for any reason, and without prejudice to further treatment. A patient can withdraw their consent to participate in the study at their own request or be withdrawn from participation in the study at the request of their legally authorized representative at any time for any reason.
- e. Privacy and confidentiality issues: Consent will be obtained by the study personnel in a private location within the TVC. No PHI will be collected prior to obtaining informed

consent. The PI and his research staff will have access to this information. Consent forms will be maintained in a locked cabinet in the GI clinical research office. PHI will be collected during the course of this research study from the medical records of consented individuals. Initially, an inclusion log will be created and maintained by the study staff. This log will contain subject initials, medical record numbers, assigned study number and date of inclusion. The only person who will have access to this inclusion log is the PI and study coordinator. The data collected will be entered into a REDCap database (attached) and will not include any information that could link the data to a specific individual. This database will be maintained by the research staff and raw data as well as results will be held by the GI Clinical Research Office indefinitely. The PI, other key study staff and statistician will have access to the REDCap database.

- f. Follow up: patients will have follow up at 3 and 6 months after initiation of the study followed by their regularly scheduled appointments after completion of the study.
- **D. Data Analysis:** paired t-test will be used for data analysis. Preparation of data listings, tables, and overall statistical support for generation of the data will be managed independently by a statistician who will remain isolated from the clinical personnel involved in the study operations.

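### The Aims ask whether ropinirole works, but the design's only controlled comparison is ropinirole against vitamin E; the aim, the test and the reading of a null should be tied to that contrast

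*Combined protocol and SAP*

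**What the plan says.** Two aims appear. Section I, Aims, is to "evaluate the efficacy of Ropinirole in treatment of muscle cramps in patients with cirrhosis". Section II, Background and Rationale, puts it differently: "Our aim is to compare the efficacy of Ropinirole, to Vitamine E in the treatment of these cramps in cirrhotic patients".

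Under Procedures, the design is a randomised crossover of 60 patients, 30 per sequence. Study procedures allocates them to "group A (Vitamin E 400 I.U) or group B (Ropinirole" for 3 months and then switches them. No placebo arm or untreated period is described. Patients qualify if they are adults with cirrhosis "who self-report regular muscle cramping". The survey is given "in the beginning of the study period and 3 and 6 months after study initiation".

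The whole analysis method in D. Data Analysis is that a "paired t-test will be used for data analysis". The pair, the sidedness and the significance level are not stated. There is no equivalence or non-inferiority margin and no rule for reporting a non-significant result.

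On vitamin E, Section II reports one result in cirrhosis, in 23 patients: "oral vitamin E (tocopherol acetate) 200 mg t.i.d. significantly improved the frequency, duration and pain associated with nocturnal cramping without untoward effects". It also cites a comparison of quinine with vitamin E that "found reduction in frequency of leg cramps to 3.6 and 3.3% respectively (95% confidence interval, -3.8, +3.2), suggesting similar efficacy".

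**The concern.** Three surveys per patient allow three pairs: baseline with ropinirole, baseline with vitamin E, and ropinirole with vitamin E. Only the last is controlled by randomisation, yet the first is the one that most directly fits the Section I aim. Patients enter because they report regular cramping, so some improvement without any drug effect is plausible.

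Suppose neither drug works and cramps ease for other reasons. Scores then fall from baseline in both periods and the drugs do not differ. Under the present text, that result could be reported as ropinirole being effective and similar to vitamin E. The background section already reads an interval that spans zero as similar efficacy, so this way of reading a null is familiar to the authors. The evidence it summarises for vitamin E in cirrhosis describes no comparator. The documents therefore give no controlled result that would let a null be read as both drugs working.

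**Working it through.** The plan has no sample-size calculation or other figure to reproduce on this point. What follows is illustration.

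**Inputs from the documents:** n = 60 (30 per sequence); surveys at baseline, 3 and 6 months; paired t-test.

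**Assumptions:** two-sided 5% test; both drugs inert; a non-drug fall *g*, in SDs of the within-patient difference, of 0.2, 0.3 or 0.4; correlation 0.5 between any two surveys of the same patient. At that correlation the SD of a difference is √(2 × (1 − 0.5)) = 1 score SD, so the two scales coincide.

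**Step 1. Baseline against ropinirole.** A false finding in ropinirole's favour has probability P(T > t), where t is the 97.5% point of Student's t with n − 1 = 59 degrees of freedom (2.001). T is noncentral t with noncentrality g√n.

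| Assumed fall *g* | g√60 | False finding for ropinirole |
|---|---|---|
| 0 | 0 | 2.5% |
| 0.1 | 0.775 | 11.5% |
| 0.2 | 1.549 | 33.1% |
| 0.3 | 2.324 | 62.8% |
| 0.4 | 3.098 | 86.2% |

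Sensitivity at g = 0.3:
- With 48 completers (an assumed 20% loss) the rate is 53.0%.
- For a fall of 0.3 score SD and correlation 0.3, the standardised fall is 0.3/√1.4 = 0.254 and the rate is 48.9%.
- For the same fall and correlation 0.7, it is 0.3/√0.6 = 0.387 and the rate is 83.9%.

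**Step 2. The misleading pattern as a whole.** This is both drugs significantly better than baseline and no significant difference between them. By simulation (40,000 trials per setting, both drugs inert), it arises in about 18%, 46% and 75% of trials at falls of 0.2, 0.3 and 0.4 SD.

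**Step 3. Ropinirole against vitamin E.** A fall that is the same on both drugs drops out of the difference, so the false-win rate is nominally 2.5% (2.4% to 2.7% in the simulations). This depends on three conditions.
- *Equal non-drug effect on both drugs.* If expectation favours ropinirole by 0.2 SD, the Step 1 formula applies with 0.2 and the false-win rate is 33%.
- *Balanced sequences.* Suppose improvement continues into the second period, shifting each patient's difference by 0.3 SD, towards ropinirole when it comes second and towards vitamin E when that does. With 28 completers taking ropinirole second and 20 taking it first, the mean is biased by 0.3 × (28 − 20)/48 = 0.05 SD and the false-win rate is about 4.4%. With 30 and 18, the bias is 0.3 × 12/48 = 0.075 SD and the rate about 6.1%. With 30 and 30 the bias is zero and the rate about 2%.
- *No carryover* between periods.

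**Step 4. What a null would show.** The 95% half-width for the direct contrast is t/√n: 2.001/√60 = 0.26 SD with 60 completers, and 2.012/√48 = 0.29 SD with 48. A result centred on zero is thus compatible with a difference of about a quarter of an SD either way, and no margin is given to judge it by.

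**The case against.** The strongest reply is that the plan never says it will test against baseline. Section II states the comparative aim, the design is a crossover, and every patient takes both drugs. In that setting a paired t-test most naturally means drug against drug. This stands. The 33% to 86% figures depend on a pairing that the plan permits but does not choose, and on a fall that the documents do not give. A reader might infer that a baseline analysis is planned; the text does not support that.

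A second reply is that the direct contrast is not a complete cure. This also stands. No blinding is described, ropinirole comes by prescription while the research office supplies vitamin E, and the outcome is a survey, so expectations could differ between the drugs. Step 3 shows what that could do.

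A third is that the background sentences are short summaries of studies that cannot be read here. The 23-patient study may have had a control that the summary omits. The sentences show how this protocol presents evidence; they do not establish how the trial will be reported.

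Two stronger readings should also be resisted. One is that the trial cannot support ropinirole's efficacy at all. A significant win over vitamin E would support it if vitamin E is no worse than no treatment and the conditions in Step 3 hold. The other is that 400 IU is too weak a comparator. The protocol does not say how often it is taken, so the documents do not show this.

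What survives is that the two aims differ, the pair is unnamed and a null has no reporting rule.

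**Conclusion.** The point holds in a limited form. Without a placebo or untreated period, the design answers the Section II question and not the Section I question as worded, and the analysis sentence does not tie the test to the answerable one. If the baseline pair were used with two inert drugs and 60 completers, an assumed non-drug fall of 0.2 to 0.4 SD would produce a false finding for ropinirole in 33% to 86% of trials. The direct contrast holds near 2.5% only under equal expectation, no carryover and balanced completers. The size therefore rests on assumptions. The logical gap does not: it can be read from Sections I and II, Study procedures and Data Analysis. It should be closed before analysis, since it determines what the trial may conclude and leaves the pair open to choice after the data are seen.

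**What to change.** 1. **Section I.** Reword the aim: *to test whether ropinirole reduces muscle cramps more than vitamin E in patients with cirrhosis*. This brings it into line with Section II.

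2. **D. Data Analysis.** Replace the test sentence with: *The paired t-test compares each patient's survey result at the end of the ropinirole period with that at the end of the vitamin E period (two-sided 5%, with 95% confidence interval). Ropinirole will be described as more effective than vitamin E only if this difference is significant in its favour. A non-significant difference will be reported with its interval and not described as similar efficacy or as both treatments working. Changes from baseline are descriptive.*

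The cost is text edits: no added patients, visits, surveys, drug or placebo. The sponsor gives up efficacy claims that rest on improvement over baseline or on a null, neither of which this design can support. Keeping the Section I aim as worded would call for a placebo or untreated period, a much larger change that is not requested. These edits do not deal with differing expectations of the two drugs, so that limitation should accompany any reported win.

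### The only planned analysis, a paired t-test, ignores period in a two-period crossover: a common shift between months 3 and 6 would cost power, and would bias the result if the sequences finish unequal

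*Combined protocol and SAP*

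**What the plan says.** The Procedures section gives the design as a "Prospective Randomized cross-over design", and B. Sample gives the allocation as "30 in Group A; 30 in Group B". Under C. Study procedures, item a, Group A starts on vitamin E and Group B on ropinirole. Each stays on its first treatment for three months, "at which time they will be switched to the other group". The survey is given "in the beginning of the study period and 3 and 6 months after study initiation", so month 3 closes the first period and month 6 the second.

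The entire method under D. Data Analysis is "paired t-test will be used for data analysis". The text does not say which two measurements form the pair. No section mentions a period or sequence term, a model that includes one, or a rule for missing data or replacement of withdrawals. Item d of C. Study procedures states: "Patients may withdraw from the study at any time for any reason".

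**The concern.** In a two-period crossover, period and treatment are confounded within each patient: Group A always meets ropinirole second and Group B always meets it first. Anything that moves all patients' results between months 3 and 6 therefore raises the ropinirole-minus-vitamin E difference in one group and lowers it in the other. Randomising the order is what allows that shift to be removed. A paired t-test that pools all patients does not use the order.

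With equal sequences, the shift cancels from the estimate but stays in the estimated variance, so power is lost. With unequal sequences it no longer cancels, and part of a time trend is reported as a drug effect. The direction depends on which sequence loses more patients. Only a shift common to all patients matters here, because patient-specific change is already part of the ordinary error.

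**Working it through.** **Inputs from the documents.** Two sequences of 30 (B. Sample); switch at month 3 and surveys at months 0, 3 and 6 (C. Study procedures, item a); paired t-test (D. Data Analysis). There is no stated sample-size calculation to reproduce.

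**Assumptions.** The pair is each patient's ropinirole result and vitamin E result, which fits the comparison set out in II. Background and Rationale. The test is two-sided at 5%. The unit is the within-sequence SD of the difference, σ = 1. The common shift π runs from 0 to 1 SD. There is no carry-over, and dropout is unrelated to outcome.

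**Model.** Let D be ropinirole minus vitamin E, τ the drug effect, and π the month 3 to month 6 shift.

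- Group A: D is month 6 minus month 3, with mean τ + π.
- Group B: D is month 3 minus month 6, with mean τ − π.
- Pooled mean of D: τ + π(nA − nB)/(nA + nB).
- Variance seen by the paired test: about 1 + π² × 4nAnB/(nA + nB)², which is 1 + π² at 30/30.
- Adjusted estimate: month 6 minus month 3 has mean τ + π in A and −τ + π in B. Half the A-minus-B difference is τ, so π drops out. Its SE is 0.5 × √(1/nA + 1/nB), with nA + nB − 2 df.

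**Reference effect.** At 30/30 the adjusted SE is 0.5 × √(2/30) = 0.129. From the noncentral t with 58 df, 80% power needs τ = 0.368 SD.

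**Equal completers, 30/30** (simulation, 100,000 trials per setting; bias zero; true SE 0.129):

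| π (SD) | Paired-test power | Type I error | Mean estimated SE |
|---|---|---|---|
| 0.1 | 80% | 5.0% | 0.129 |
| 0.25 | 78% | 4.2% | 0.133 |
| 0.5 | 73% | 2.8% | 0.144 |
| 0.75 | 63% | 1.4% | 0.161 |
| 1.0 | 51% | 0.5% | 0.183 |

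The formula agrees: at π = 0.5, √(1.25/60) = 0.144. The adjusted test stays at 80% power and about 5% error throughout.

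**Unequal completers:**

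- 28/24: bias = π × 4/52 = 0.077π, or 0.038 SD at π = 0.5. Type I error is 4.5% falling to 1.4% as π goes from 0.25 to 1.0. At π = 0.5 with the bias opposing the effect, power is 55% against 74% adjusted.
- 28/20: bias = π × 8/48 = 0.167π, or 0.083 SD at π = 0.5, which is 0.083/0.368 = 23% of the effect. Type I error is 5.2% to 5.6%. At π = 0.5, power is 81% if the bias favours the effect and 40% if it opposes it, against 69% adjusted.
- 30/20: bias = π × 10/50 = 0.2π, or 0.10 SD at π = 0.5 (27% of the effect). Type I error is 7.1%, 8.1% and 8.7% at π = 0.5, 0.75 and 1.0. At π = 0.5, power is 85% or 37% by direction, against 70% adjusted.

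Simulated bias matched the formula in every setting. In these settings the adjusted test was unbiased with about 5% error.

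**The case against.** The strongest reply has four parts.

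1. **The pair is inferred.** A baseline-versus-follow-up pair is possible on the text. That is fair, and the figures above would not then apply. It does not rescue the plan: a before-and-after test within a treatment would count any time shift as drug effect even at 30/30.
2. **Nothing is invalid at the planned allocation.** This stands. At 30/30 the estimate is unbiased and the test errs on the conservative side. A material loss needs a large shift: π = 0.5 already exceeds the assumed drug effect, and the documents give no reason to expect it. They do not rule it out either, and the method has to be fixed before the shift is known.
3. **Clear type I inflation needs an extreme split.** This also stands. At 28/24 the error is below 5% and at 28/20 it is close to 5%; it reaches 7% to 9% only at 30/20 with a large shift. Bias and direction-dependent power appear at milder splits.
4. **Adjustment does not protect against informative dropout.** Correct. In a deliberately severe example, there is no drug or period effect, the between-patient SD equals the SD of D, and the 10 Group B patients with the lowest first-period values leave (30/20). The adjusted test then has bias of about 0.11 SD and type I error of about 12%. The claim of no bias is therefore limited to dropout unrelated to outcome. That is a separate missing-data problem, which the paired t-test does not solve either.

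**Conclusion.** The concern holds and should be fixed. With equal sequences the harm is lost power only: about 2 points or less for shifts up to 0.25 SD, 7 points (80% to 73%) at 0.5 SD and 29 points (80% to 51%) at 1.0 SD, with no added false-positive risk. With unequal sequences the estimate is biased by π(nA − nB)/(nA + nB), in a direction that cannot be known in advance. The algebra is exact under the stated model. The sizes rest on an assumed shift, completer split, effect and pairing, none of which the documents give. The omission does not by itself make the trial invalid.

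**What to change.** Replace the method sentence in D. Data Analysis with:

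> Ropinirole will be compared with vitamin E using the month 3 and month 6 survey results. The within-patient period differences (month 6 minus month 3) will be compared between Group A and Group B by a two-sample t-test. The difference (Group A minus Group B) will be halved to give the ropinirole-minus-vitamin E effect, reported with a 95% CI.

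The sponsor needs to insert which survey result is analysed.

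A linear mixed model with treatment, period and sequence and a random patient effect is an acceptable alternative. On one simulated complete 30/30 data set the two gave the same estimate (0.0575, SE 0.127). After the second period was removed for 10 Group B patients they differed (−0.076 for one, −0.037 for the other), because the model can also use patients with one period. One of the two should therefore be named as primary in advance. The paired t-test may stay as a supporting analysis.

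The cost is wording and one degree of freedom (59 to 58), with no new data or patients. If there is in fact no period shift, the power given up is under 0.1 point at 30/30, 0.3 at 28/24 (73.7% against 74.0%), 1.3 at 28/20 (69.1% against 70.4%) and 1.8 at 30/20 (70.4% against 72.2%). The change does not deal with carry-over, which is a separate matter.
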